## 5.3 Study Population Characteristics

### 5.3.1 Study Enrollment

Patient enrollment, eligibility, and study populations are summarized by frequency and percentage of patients.

### 5.3.2 Patient Disposition

The disposition of patients (based on the reasons reported for treatment and study discontinuation) is summarized by frequency and percentage of patients.

### **5.3.3 Protocol Deviations**

Protocol deviations are categorized by Theradex Oncology and Bayer HealthCare BioPharma as minor protocol deviations (a protocol deviation that does not have a significant impact on the research participant's rights, safety, or welfare; the integrity of the data; nor substantially alter risks to subjects as determined by IRB), and major protocol deviations (a deviation from the protocol, International Council for Harmonization Good Clinical Practice [ICH-GCP], or local requirements that may impact patient safety, affect the scientific integrity of the trial, or the patient's willingness to participate in the trial).

### **5.3.4 Prior Systemic Anti-Cancer Therapy**

Prior systemic life prolonging anti-cancer therapies including treatment intent, the number of regimens (1,  $\geq 2$ ) administered, best response, and discontinuation reason along with therapy types (Abiraterona acetate, prednisone, enzalutamide, apalutamide, darolutamide, docetaxel, bicalutamide, flutamide, nilutamide, Radium-223, sipuluecel-t, and systemic radiotherapy) as allowed based on exclusion criteria, will be summarized by frequency and percentage of patients within each category.

### **5.3.5 Prior Radiotherapy and Prior Surgery**

Prior radiotherapy including intent, type, relieve skeletal symptom, irradiated location, best response, and prior surgeries will be summarized by frequency and percentage of patients within each category.

### **5.3.6 Demographics and Baseline Characteristics**

Demographic data including age categories ( $<75$ ,  $\geq 75$ ), sex, race, ethnicity, CRPC metastatic status and Karnofsky performance scale (KPS) are summarized by frequency and percentage of patients within each category.

Age is also summarized using descriptive statistics as a continuous variable. Dominant hand and education level are summarized by frequency and percentage of patients within each category.

## **5.4 Efficacy Analyses**

The primary analysis for the lead-in phase of the study will occur when the last participant has been on the study for at least 24 weeks, unless the

participant discontinued due to being lost to follow-up, withdrawal, or death.

The final analysis for the randomized phase of the study will occur when the last participant has been on the study for at least 52 weeks after the start of study intervention, unless the participant discontinued due to being lost to follow-up, withdrawal, or death.

#### **5.4.1 Primary Efficacy Endpoint Analysis**

There is no primary efficacy endpoint in this study.

#### **5.4.2 Secondary Efficacy Endpoint Analyses**

The study is not powered to test a specific hypothesis for efficacy, the two arms will not be formally compared for efficacy.

**Time to PSA progression** will be calculated as the time from randomization (or the date of the first dose for participants in the lead-in phase) to the time when the criteria for PSA progression (according to PCWG3) are met. The PCWG3 guideline defines PSA progression as the date that an increase of 25% or more and absolute increase of 2 ng/mL or more from the nadir are documented. For participants who had an initial PSA decline during treatment, this must be confirmed by a second value 3 or more weeks later. Kaplan-Meier methods will be used to estimate the median time to PSA progression and 95% CIs for each treatment arm.

The SAS procedure, Proc Lifetest, will be used to calculate estimates of the time to PSA progression using Kaplan-Meier methodology. The Kaplan-Meier curves for the time to PSA progression will be presented. Confidence intervals (CIs) for the median duration times are calculated using the method by Brookmeyer and Crowley [2]. CIs for point estimates of the survival distribution are calculated using the method by Kalbfleisch and Prentice [3]. Patients who did not have a PSA progression event at the time of analysis (either for lead-in or randomization phase) will be censored at the date of the last assessment showing no evidence of PSA progression

#### **PSA response at 24 and 52 weeks**

Number (%) of subjects achieving 30% / 50% / 90% PSA reduction from baseline will be summarized for the time period up to and including each visit.

**Overall survival (OS)** is defined as the time from the date of randomization (or the date of the first dose for participants in the lead-in phase) to death due to any cause. Participants who are still alive will be censored at the last date known to be alive. The Kaplan-Meier method will be used to estimate the median survival and survival rate at the 1-year timepoint along with the 95% CI for each treatment arm of the randomized phase (not to be analyzed in lead-in phase).

A listing of deaths on study or within 30 days post-last dose will also be produced.

### 5.4.3 Other

Additional subgroup analyses will be performed, as specified below. Time to PSA progression and OS will be explored across baseline characteristic subgroups.

- Age group (< 75 vs. ≥ 75 years)
- Number of prior systemic life-prolonging anticancer therapies (1 vs. ≥ 2)

## 5.5 Safety and Tolerability Analysis

Safety analyses are based on the Safety population. Descriptive statistics are used to summarize the safety parameters. Safety data including AEs, AESI, laboratory parameters, vital signs, exposure and KPS. The protocol schedule of events and windowing will be used for the applicable safety table assessments.

Endpoints measuring physical function, daily activity and cognitive function will also be performed on the Safety population.

### 5.5.1 Primary Endpoint Analyses

The primary variable in this study is the proportion of participants with a worsening in TUG time during the 24-week period from baseline, using the best TUG time out of the measured assessments during study visits (two or

three assessments). Worsening is defined as an increase of at least 1 second in TUG time from baseline.

The proportion of participants with a worsening in TUG time and the (exact) 95% CIs will be summarized by treatment arm. A comparison between treatment arms will be made using Cochran-Mantel-Haenszel (CMH) test adjusting for Age (<75, ≥75). A sensitivity analysis will be provided by replacing missing TUG times with ≥ 1 second increase. Primary endpoint (worsening in TUG) analysis will be performed by age (<75, ≥75), metastatic state (nmCRPC, mCRPC), Pain (yes, no pain), and opioid use (yes, no opioid use). Information on pain and opioid use will be retrieved from an examination of medical history and prior medication CRFs.

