## 2.0 Objectives and Endpoints

**Table 1 Objectives and Endpoints**

Objectives	Endpoints
Primary	

The primary objective of this study is to compare the effects of treatment with darolutamide vs. enzalutamide on physical function as assessed by the Timed Up and Go (TUG) test in participants with castration-resistant prostate cancer (CRPC).
	
Proportion of participants with a worsening in TUG time during the 24-week period from baseline. Worsening is defined as an increase of at least 1 second from baseline, using the best TUG time out of the measured assessments during study visits. (The minimum clinically important difference [MCID] in TUG time is 1 second (Davies et al. 2016)) [1].

Secondary	

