
The secondary objectives of this study are to:
 
 
• Compare the effects of treatment with darolutamide vs. enzalutamide on physical function, as assessed by the TUG test at 12 and 24 weeks, and by 52 weeks.
 
• Compare the effects of treatment with darolutamide vs. enzalutamide on physical function as assessed by Short Physical Performance Battery (SPPB) test at 12 and 24 weeks, and by 24 and 52 weeks.
 
• Assess the effects of treatment with darolutamide vs. enzalutamide on daily activity as assessed by accelerometry at 12 and 24 weeks, and by 24 and 52 weeks.
 
• Compare the effects of treatment with darolutamide vs. enzalutamide on cognitive function as assessed by Hopkins Verbal Learning Test-Revised
 
	
Physical Function:
 
 
• Proportion of participants with an increase of at least 1 second in TUG time at 12 and 24 weeks and during the 52 weeks from baseline, using the best TUG time out of the measured assessments during study visits.
 
• Time to worsening (increase of at least 1 second) in TUG time.
 
• Proportion of participants with a worsening in SPPB total score at 12 and 24 weeks and during the 24 weeks and 52 weeks from baseline. Worsening is defined as one point worsening in SPPB total score from baseline.
 
 
Daily Activity:
 
 
• Mean change from baseline in daily physical activity at 12 and 24 weeks, and during the 24 weeks and 52 weeks from baseline.
 
• Mean change from baseline in accelerometer-assessed proportion of time spent in light to vigorous physical activity (light physical activity defined as 100<AC per minute<760 and moderate-to-vigorous activity (≥760 AC per minute), at 12 and 24 weeks, and during the 24 weeks and 52 weeks from baseline.
 
 
Cognitive Function:
 
 
• Proportion of participants with a decline in cognitive function during the 24 weeks and 52 weeks from baseline, as assessed by HVLt-R, TMT, and COWA. See Table 4 for the definition of decline for each test.
 

Objectives	Endpoints

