## **5.5.2 Secondary Endpoints Analyses**

### **Physical function**

- Proportion of participants with a worsening in TUG time from baseline at 12 and 24 week study visits, and at any time up to 52 weeks will be summarized.
- TUG time (secs) and percent change from baseline will also be summarized by metastatic/non-metastatic CRPC status, pain (yes, no pain), and opioid use (yes, no opioid use).
- At each assessment, status of TUG time will be summarized as the categories of improved, stable or worsened.
- Time to worsening in TUG time will be defined as time from randomization (or time from first dose for participants in the lead-in phase) to the first date a participant had a worsening. Time to worsening in TUG time will be summarized using Kaplan-Meier methodology, and a comparison between the two arms in the randomization phase will be made using a two-sided, stratified log-rank test, stratified by Age (<75, ≥75). The hazard ratio as well as its 95% CI will be presented using a stratified Cox regression model. An unstratified analysis will also be performed. The Kaplan-Meier plots will be provided for both stratified and unstratified analyses.
- Similar to the primary endpoint, the proportion of participants with a decline of at least 1 point in SPPB total score at 12 and 24 week study visits and at any time up to 24 and 52 weeks will be summarized. SPPB

will be analyzed by age (<75, ≥75), metastatic state (nmCRPC, mCRPC), Pain (yes, no pain), opioid use (yes, no opioid use).

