**Table 4 Study Assessments for Physical Ability and Cognitive Function**

Test	Description	Possible Range of score	MCID/RCI from Baseline
Physical ability tests			
Timed Up and Go (TUG)	The TUG test is used to assess a person's mobility and requires both static and dynamic balance. It uses the time that a person takes to rise from a chair, walk three meters, turn around, walk back to the chair, and sit down.  Where possible, TUG time is to be measured by independent blinded assessors.	>1 second	1 second (Davies et al. 2016) [1]
Short Physical Performance Battery (SPPB)	The SPPB is a group of measures that combines the results of the gait speed, chair stand and balance tests.	0–12 points	0.5 points (Davies et al. 2016) [1]
Cognitive Tests			

Test	Description	Possible Range of score	MCID/RCI from Baseline
Hopkins Verbal Learning Test-Revised Total Recall (HVLTR TR)	The HVLTR is a learning and memory test, in which the participant is asked to learn and recall a list of 12 words over 3 trials.	0–36 words	±5 words (Wefel et al. 2011) [4]
Hopkins Verbal Learning Test-Revised Delayed Recall (HVLTR DR)	Spontaneous recall is assessed before and after a delay.	0–12 words	±3 words (Wefel et al. 2011) [4]
Hopkins Verbal Learning Test-Revised Delayed Recognition (HVLTR RECOG)	Recognition discriminability is also assessed after a delay. Four alternate versions of the test are used to minimize practice effects over time.	-12–+12 words	±2 words (Wefel et al. 2011) [4]
Trail Making Test (TMT) Part A (TMTA) Part B (TMTB)	
The TMTA assesses visual scanning and motor tracking requiring focused attention. Participants are required to sequentially connect numbered dots in ascending order that are randomly scattered across the test page.
 
TMTB includes a divided attention component requiring mental flexibility (i.e., executive function). On this subtest, dots with numbers and letters are randomly scattered on the test page. Participants are required to alternate between connecting numbers and letters in an ascending sequential order.
 
Both tests require the participants to complete the sequence as fast as possible. TMTA is discontinued after 3 minutes and TMTB is discontinued after 5 minutes for participants who have difficulty in order to reduce participant burden.
	1–2750 seconds 1–3750 seconds	±12 seconds ±26 seconds (Wefel et al. 2011) [4]

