## 8.0 Table 8-1 Schedule of Activities

### Lead-in phase

Table 8–1 Schedule of Activities for the Lead-in Phase (darolutamide)											
Assessment	Screening	Intervention + Observation Period								End of treatment visit (30 days after last dose) m	Survival follow-up l,n
		Week 1 Day 1 i	Week 4 j	Week 8	Week 12	Week 24	Week 38	Week 52	from Week 53: Active follow up every 3 months k,l		
Time window allowed	within 21 days prior to first dose		± 7 days	± 7 days	± 7 days	± 7 days	± 14 days	± 7 days	± 1 month	+ 1 month	± 1 month
Informed consent	X										
Inclusion and exclusion criteria	X										
Demography	X										
Full physical examination including weight (height at screening only)	X	X	X	X	X	X	X	X	X	X	
Medical & surgical history including past and current medical conditions, substance use of drugs, alcohol, tobacco and caffeine.	X										
Concomitant medication review	←----->										
Karnofsky Performance Scale	X	X	X	X	X	X	X	X	X	X	
Laboratory assessments (including liver chemistries) a	X	X	X		X	X	X	X	X	X	

Table 8–1 Schedule of Activities for the Lead-in Phase (darolutamide)											
Assessment	Screening	Intervention + Observation Period								End of treatment visit (30 days after last dose) m	Survival follow-up l,n
		Week 1 Day 1 i	Week 4 j	Week 8	Week 12	Week 24	Week 38	Week 52	from Week 53: Active follow up every 3 months k,l		
Time window allowed	within 21 days prior to first dose		± 7 days	± 7 days	± 7 days	± 7 days	± 14 days	± 7 days	± 1 month	+ 1 month	± 1 month
Serum PSA a	X	X	X		X	X	X	X	X	X	
Vital signs	X	X	X	X	X	X	X	X	X	X	
Treatment dispensing / accountability		X	←=====→								
AE review b		←=====→									
AEs of interest review, including fall c		←=====→									
Timed Up and Go assessment (TUG) d	X h	X h			X	X		X	X		
Short Physical Performance Battery (SPPB) d		X			X	X		X	X		
Accelerometry assessment e	X				X	X		X	X		
Cognitive function f		X				X		X	X		
Brief Fatigue Inventory (BFI) g		X	X	X	X	X		X			
Patient Health Questionnaire (PHQ-9)		X	X	X	X	X		X	X		
Survival status											X

X = measure/action to be performed at the time point indicated

←=====→ = measure/action to be performed continually during the time period indicated

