AE = adverse event; BFI = Brief Fatigue Inventory; COWA = Controlled Oral Word Association; CRF = case report form; HVLt-R = Hopkins Verbal

Learning Test - Revised; PHQ-9 = Patient health questionnaire-9; PSA = prostate-specific antigen; SPPB = Short Physical Performance Battery; TMT = Trail Making Test; TUG = Timed Up and Go

- a PSA will be assessed at the same time as other laboratory assessments. A time window of  $\pm$  14 days is allowed for laboratory and PSA assessments.
- b Including survival, pain, radiographic progression, metastases, and skeletal events
- c AEs of interest are fractures, falls, and hypothyroidism
- d Physical function tests include SPPB and the TUG assessment.
- e Accelerometry assessment will require the participant to wear an accelerometry device on the wrist or hip for a minimum of 7 days at each time point. The first accelerometry assessment is to be performed before the first dose (i.e. during screening).
- f Cognitive function tests include the HVLT-R, TMT, and COWA, as well as the patient-reported outcome questionnaire FACT-Cog.
- g BFI is a 5 minute self-assessment tool that identifies fatigue in cancer participants over a 24-hour period.
- h The first TUG assessment is to be performed before the first dose (either during screening or Week 1 Day 1).
- i Once the baseline procedures are completed, the first administration of study intervention will be provided at the study center and the participant will be provided with additional medication to take as scheduled through the Week 4 visit. (Each participant will be instructed to bring any remaining drug back to the center at the Week 4 visit.)
- j At this and each subsequent visit, the participant will return dispensed but unused study intervention to the investigator for recording on the CRF. Reasons for non-compliance will be recorded. A new supply of study drug sufficient to meet the dosing requirements of each participant will be dispensed.
- k Participants remaining on treatment beyond Week 52 will continue, where possible, to receive study intervention and assessments until the final evaluation of the randomized phase (i.e. at Week 52 for the last participant, see Protocol Section 4.4.1)
- l Prior to the final evaluation of the randomized phase of the study, all participants will go into Week 53 active follow-up or survival follow-up as applicable.

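### Does the SAP leave open whether the best TUG time is taken within a visit or across visits?

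*SAP*

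**What the plan says.** SAP section 5.5.1 defines the primary variable over the 24-week period "using the best TUG time out of the measured assessments during study visits (two or" three), with worsening set at an increase of at least 1 second from baseline. SAP Table 1 gives the primary endpoint the same rule, "using the best TUG time out of the measured assessments during study visits", without a count. Table 1 also attaches it to the secondary TUG endpoint: "at 12 and 24 weeks and during the 52 weeks from baseline, using the best TUG time".

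SAP section 5.5.2, under Physical function, carries out that secondary endpoint as worsening at the Week 12 visit, at the Week 24 visit, "and at any time up to 52 weeks will be summarized". It also reports status by occasion: "At each assessment, status of TUG time will be summarized as the categories of improved, stable or worsened".

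The test description in SAP Table 4 is of one timed performance ("It uses the time that a person takes to rise from a chair, walk three meters, turn around" and so on) and mentions no repeats. In the schedules of activities (SAP Tables 8-1 and 8-2), the row "Timed Up and Go assessment (TUG" has follow-up marks at Weeks 12, 24 and 52 and then in active follow-up from Week 53. Protocol section 9.4.2 calculates the TUG change at each assessment and counts decline by 24 weeks. It has no best-of rule.

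**The concern.** The word assessment has to carry two meanings. Elsewhere in the SAP a TUG assessment is an occasion, as in the status summary quoted above and in the schedule footnote: "The first TUG assessment is to be performed before the first dose (either during screening or Week 1 Day 1"). Read that way in section 5.5.1, the best time could be the fastest across follow-up visits, and a participant would count as worsened only if every visit was at least 1 second slower than baseline. The count of two or three seems to fit, since there are two follow-up TUG visits by Week 24 and three by Week 52. Section 5.5.1 also lacks the any-time wording that section 5.5.2 uses, and no passage describes repeat trials within a visit.

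If an analyst took that reading, a participant who slowed at Week 12 and recovered by Week 24 would be left out of the primary endpoint yet would be an event in time to worsening, which uses the first date. The lead-in rate would be too low, and that rate informs the sample size of the randomized phase (SAP section 3.4).

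**Working it through.** **1. The plan's own power figure.** Inputs from SAP section 3.4: about 120 participants, 10% drop-out, 20% against 40% worsening, one-sided alpha 10%. SAP section 3.3 gives 1:1 allocation. Evaluable: 120 × 0.9 = 108, or 54 per arm. With unpooled variance, z = 0.20 / √[(0.2×0.8 + 0.4×0.6)/54] − 1.2816 = 0.20/0.0861 − 1.2816 = 1.042, so power is 85.1%. The pooled formula gives 84.4%. The stated 85% reproduces.

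**2. What the two readings would give.** Call them A (best trial within a visit; worsened if either Week 12 or Week 24 is at least 1 s slower) and B (best across visits; worsened only if both are). If p is the rate at each visit, A = 2p − P(both) and B = P(both), so B can never exceed A. P(both) is taken from a bivariate normal model with correlation r between the two changes. The documents give no value for r, so the range is an assumption.

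| r | A = 30%: B | A = 20% / 40%: B | Power under B, 54 per arm (pooled) |
|---|---|---|---|
| 0.5 | 8.1% | 4.3% / 13.1% | 64% |
| 0.7 | 12.0% | 6.8% / 18.4% | 71% |
| 0.8 | 14.8% | 8.6% / 22.0% | 74% |
| 0.9 | 18.8% | 11.4% / 26.9% | 78% |
| 0.95 | 21.8% | 13.7% / 30.6% | 80% |

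Check at r = 0.7 in the 40% arm: p = 29.2%, and 2 × 29.2 − 18.4 = 40.0.

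This table treats 20% and 40% as either-visit rates. SAP section 3.4 states them at 24 weeks. If they are the rates at each single visit, then for r from 0.5 to 0.9 reading B gives 8.7% / 23.9% to 15.0% / 33.1%, with power 81% to 83%. That is 1 to 3 points below 84%.

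**3. Which reading the text supports.**

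- *Single-visit endpoints.* Table 1 applies the best-time rule to Week 12 and Week 24 taken singly. A best across visits has no meaning at one visit; a best among trials does.
- *The 52-week endpoint.* Table 1 applies the same words to it, and section 5.5.2 carries it out as worsening at any time. Reading B would require slowing at all visits, which contradicts that.
- *The link to the primary endpoint.* Section 5.5.2 introduces the SPPB analysis as similar to the primary endpoint and counts a decline at any time up to 24 and 52 weeks.
- *The count.* Section 5.5.1 covers 24 weeks only, and the schedule has two follow-up TUG visits in that time. Three is reached only by counting baseline, and a best time that includes baseline can never be 1 second worse than baseline. Week 52 belongs to a different endpoint.
- *The protocol.* Section 9.4.2 takes the change at each assessment and counts decline by 24 weeks. SAP section 6.0 declares no change to planned analyses.
- *Time to worsening.* It uses the first date of worsening, which agrees with A.

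**4. Unequal trial counts under A.** The number of trials is not fixed. Assume a within-visit SD of 0.3 to 1.0 s, an SD of true change of 1.0 to 1.5 s, a correlation of true change of 0.5 or 0.8, and independent normal trials, with a 30% rate when every visit has two trials. If each visit has two or three trials at random, the simulated rate is 29% to 30%. Three trials at baseline and two at follow-up throughout would give 32% to 37%; the reverse would give 22% to 28%. Nothing in the documents suggests such a systematic mismatch.

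**The case for a change.** The strongest case for a change is that a programmer should not have to infer how the primary endpoint is derived. The protocol has no best-of rule to explain the term. The SAP's baseline definition (section 5.1.1) takes the last measurements before dosing and does not mention the best trial. The missing-data sensitivity analysis also depends on the reading: replacing a missing Week 12 time with a 1-second increase makes the participant an event under A, but changes nothing under B if Week 24 has not worsened.

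It stands that no sentence states the within-visit rule or extends it to baseline. It does not stand that the reading is open, because B conflicts with the SAP's own single-visit and 52-week endpoints. A mistaken derivation would also show. Section 5.5.2 reports worsening at Week 12 and Week 24 separately, status at each assessment and time to first worsening, and section 5.1 says that all raw data will be listed. A primary rate below either single-visit rate would be noticed at once. The annotated eCRF that the SAP lists among its sources may show the trial fields, but the conclusion does not depend on it.

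**Conclusion.** This is a missing detail that analysts would fill correctly: the fastest trial at each visit, baseline included, and worsening if Week 12 or Week 24 is at least 1 second slower than baseline. The drop from 30% to between 8% and 19%, and power of 64% to 78%, are sound arithmetic for r between 0.5 and 0.9. They describe a derivation that the SAP's own text rules against, and they rest on a correlation that the documents do not give. They are not an effect of following the plan.

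A table of trial counts, or a sensitivity analysis limited to the first two trials, would gain little: random variation in counts moves a 30% rate by about one point at most under the stated assumptions. The endpoint and sample size for the randomized phase are to be reassessed after the lead-in phase in any case (SAP section 3.1). A sentence spelling out the rule would be tidy but optional.
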